## **9.2.2 Specifications Of Safety Analyses**

### **9.2.2.1 Adverse Events**

- An untoward medical occurrence during a clinical investigation, whether or not related to the investigational medical device, is an adverse event (AE).
- AEs will be coded using MedDRA version 24.0 or higher. System Organ Class (SOC) and Preferred Term (PT) will be reported.
- The investigator will grade the severity of the AE (mild, moderate, severe). AEs with missing severity will not be imputed.
- Adverse events will be summarized using frequency tables in descending order of incidence by SOC and PT unless otherwise specified. If a subject has the same AE reported more than once, the highest severity of this AE for that subject will be reported.
- For adverse events of special interest, the CEC assessment and investigator assessment will be performed, and the results of the two assessments will be presented separately.

### **9.2.2.3 Concomitant medication**

- Concomitant medications are defined as medications that were taken by the patient until or until after randomization.
- Concomitant medications will be summarized by treatment group and the number and percentage of subjects will be listed by medication name.

## 12. APPENDICES

### 12.1 Appendix 1: Treatment Period and Study Period

Treatment Period and Study Period						
Study Day						
Time points and assessment windows						
Study Flow Chart						
STUDY PROCEDURES	Screening a	Baseline	Follow-up Period			
Visit Time b	V0	V1	V2	V3	V4	V5
	-14 to Day 0	Day 0	At discharge	Day 30	Day 90	Day 360
Informed Consent	X					
Demographics	X					
Inclusion/Exclusion Criteria		X				
Medical History and Prior Medications	X					
Vital signs	X			X	X	X

Treatment Period and Study Period						
Admission examination c	X					
CT/MRI d	X				X	X
DSA e		X				
Randomized and treated		X				
Treatment and nursing costs			X		X	X
Efficacy Endpoints					X	X
Serious Adverse Events					X	
SDH-related death events					X	
Procedure-related serious complications					X	
Concomitant medication/treatment			X	X	X	X
MRS scale	X				X	X
EQ-5D Scale	X				X	X

A Screening visit and baseline visit may be on the same day

B V3 visit window is  $\pm 7$  days, V4 visit window is  $\pm 14$  days, and V5 visit window is  $\pm 30$  days

c Blood routine (red blood cell count, white blood cell count, platelet count, hemoglobin), coagulation function (APTT, INR), liver and kidney function (ALT, AST, BUN, Cr), Electrolytes (potassium, sodium, chloride, calcium), fasting blood glucose; Women of childbearing potential will need a negative urine HCG test to be enrolled. Those women of childbearing potential with positive or missing pregnancy test will not be included.

d CT is mandatory, MRI optional, and MRI examination may be performed at the physician's discretion according to the patient's condition

E Performed only in the MMA embolization group

Acceptable Time Windows for Follow-up Period

Treatment Period and Study Period	
Time Point	Acceptable Time Window
V3	±7 days
V4	±14 days
V5	±30 days

## 12.2 Appendix 2: Data Display Standards and Handling Conventions

Data Display Standards and Handling Conventions
Criteria for Data Presentation

 
● Numerical data will be reported with precision collected in the eCRF.
 
● Precision reported from non-eCRF sources will follow dMed 's statistical principles but may be adjusted to clinically interpretable decimal places (dp.).
 
● Derived data and their statistics will be 1 decimal place more than the original data and the corresponding statistics. For example, if the raw data collected contains 1 decimal place, derived data in the listings will be presented to 2 decimal places. Therefore, the average number of derived data will be presented with 3 decimal places, minimum and maximum with 2 decimal places, standard deviation with 4 decimal places, and so on.
 
● Precision validity and display utility will be considered in determining the number of decimal places displayed. Therefore, if the number of decimal places is too large to add additional information, the reported data will retain the appropriate number of decimal places. The maximum number of decimal places reported for any summary statistic should be 4, unless otherwise specified.
 
● The maximum number of decimal places can be directly applied to the ADaM dataset.
 

Data Display Standards and Handling Conventions		
Precision		
Name	Description	Decimal place (dp)
N	Number of subjects in treatment group	Always shown as 0 dp.
N	Number of subjects with non-missing results	Always shown as 0 dp.
%	Percent	Categorical data shown as 1 dp.
Mean	Arithmetic mean	1 dp. more than original data
SD	Standard deviation	2 dp. more than original data
Median	Median	1 dp. more than original data
Min.	Minimum value	Corresponds to raw data
Max.	Max	Corresponds to raw data
SE	Standard Error	1 dp. more than statistical parameters
95% CI	95% confidence interval	1 dp. more than statistical parameters
P value	P value	3 dp., or < 0.001

Baseline Definitions and Derivations
The last non-missing measurement/assessment prior to the randomization date will be used as the baseline measurement unless specified.
Measurements/assessments will be considered (if not missing) at baseline if performed on the same day as randomization.

 
● Change from baseline = value at post-treatment visit – baseline if there is no specific formula or medical requirement in the protocol.
 
● Percent change from baseline = <math>100\% * (\text{treatment value at post visit} - \text{baseline})/\text{baseline}</math>
 

General Data Display Standards and Handling Conversion

Data Display Standards and Handling Conventions	
Planned and Actual Time	

 
● Unscheduled visits and visits outside protocol-specified windows (ie, documented as protocol deviations) will be included in listings only, unless otherwise specified.
 
	
Proportion Calculation	

 
● Percent of zero counts will not be shown.
 
● Percentages will be calculated based on the number of participants in the analysis population of interest, unless specifically stated. Missing observations will also be included in the denominator calculation.
 
	
Time Transition of segments	

 
● 1 year = 365.25 days
 
● 1 month = 30.4375 days
 
● 1 week = 7 days
 
	

## 12.3 Appendix 3: Handling of Early Withdrawals and Missing Data

Handling of Early Withdrawals and Missing Data			
Subjects Withdrawn Early			
Subject substitution: Subjects will not be replaced regardless of withdrawal from the trial for any reason.			
Handling of missing data			
Analysis	Death within 104 days (90 days + 14 days)	Visit out of window	No 90-day (± 14 days) visit data

Handling of Early Withdrawals and Missing Data			
Primary analysis	As if an event occurred	Observed measurements for out-of-window visits will be treated as 90-day results	Multiple imputation*
Sensitivity 1	As if an event occurred	As No Event	As if an event occurred
Sensitivity Analysis 2	As if an event occurred	As No Event	As No Event

\*If percentage of missing primary endpoint is less than 5%, multiple imputation will not be performed and missing data will be regarded as no event.

#### **SAS Code Sample:**

```
proc mi data=im1 seed=1234 n impute=20 out=im2
round=....1
min=....0
max=....1;
;
by trtan;
var sex age bmi basemrs basemth aval;
mcmc chain=multiple nbiter=200 niter=100;
run;
```

```
proc sort data=im2;
```

```
by _imputation_ trtan usubjid siteid;
run;
```

```
proc transpose data=im2 out=im2_t(rename=(_name_=avisit coll=aval));
```

```
by _imputation_ trtan usubjid siteid;  
var v1 v2;  
run;
```

```
proc sql noprint;  
create table im2_count as  
select distinct  
    _imputation_,  
    trtan,  
    avisit,  
    aval,  
    count(*) as count  
from im2_t  
group by _imputation_,trtan,avisit,aval  
order by _imputation_,trtan,avisit,aval  
;  
quit;
```

```
/*clopper-pearsen 95%ci*/  
ods select none;  
proc freq data= im2_count;  
    by _imputation_ trtan avisit;  
    table aval / binomial (cl=exact) alpha=0.05;  
    weight count;
```

```
ods output binomial=binomial;
```

```
run;
```

```
ods select all;
```

```
proc transpose data=binomial out=binomial_t;
```

```
by _imputation_ trtan avisit;
```

```
var nvalue1;
```

```
id label1;
```

```
quit;
```

```
proc sort data=binomial_t;
```

```
by trtan avisit _imputation_;
```

```
run;
```

```
ods select none;
```

```
proc mianalyze data=binomial_t;
```

```
by trtan avisit;
```

```
modeleffects proportion;
```

```
stderr ase;
```

```
ods output parameterestimates=binomial_t_pool;
```

```
run;
```

```
ods select all;
```

```
/*mn*/
```

```
proc freq data=im2_t;  
  by _imputation_ ;  
  tables trtan *aval / commonriskdiff (cl=score test=score) riskdiff (cl=mn);  
  ods output commonpdifftests=commonpdifftests1 commonpdifff=commonpdiffl  
    pdiffcls=pdiffcls1 riskdiffcol1=riskdiffcol11;  
run;
```

```
data riskdiffcol11;  
set riskdiffcol11(where=(row="difference"));  
run;  
proc sort data=riskdiffcol11;  
  by _imputation_ ;  
run;
```

```
proc mianalyze data=riskdiffcol11;  
  modeleffects risk;  
  stderr ase;  
  ods output parameterestimates=pest1_pool;  
run;
```

```
/*cmh*/
```

```
*** perform cmh test;  
proc freq data=im2_t;
```

```
tables strata*trtan*aval/cmh;  
ods output cmh=cmh;  
by _imputation_;  
run;  
*** apply wilson-hilferty transformation to the cmh statistic and  
standardize the resulting normal variable;
```

```
data cmh_wh;  
set cmh(where=(alhypothesis="general association"));  
cmh_value_wh=((value/df)**(1/3) - (1-2/(9*df))/sqrt(2/(9*df));  
cmh_sterr_wh = 1.0;  
run;
```

```
*** combine results;  
proc mianalyze data=cmh_wh;  
ods output parameterestimates=mian_cmh_wh;  
modeleffects cmh_value_wh;  
stderr cmh_sterr_wh;  
run;
```

```
proc sql noprint;  
create table im2_count2 as  
select distinct  
_imputation_, avisit, siteid, trtan, aval,
```

```
count(*) as count
from im2_t
group by _imputation_,avist,siteid,trtan,aval
order by _imputation_,avist,siteid,trtan,aval
;
quit;
```

```
ods select none;
proc glimmix data=im2_count2;
  by _imputation_ avist;
  class siteid trtan aval;
  model aval/count=trtan / solution;
  random intercept / subject=siteid;
  ods output parameterestimates=parameterestimates;
run;
```

```
ods select all;
proc sort data=parameterestimates(where=(trtan=1)) out=parameterestimates1;
  by trtan avist _imputation_ ;
run;

ods select none;
proc mianalyze data=parameterestimates1;
  by trtan avist;

```

```

modeleffects estimate;
stderr stderr;
ods output parameterestimates=parameterestimates1_pool;
run;
ods select all;

```

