3.1 Overall Study Design

This is a multicenter, phase III, prospective, randomized, open-label, and parallel controlled clinical study with blinded outcome assessment. Approximately 722 cases will be included in this study in China, with a ratio of 1:1 for randomization into the MMA embolization and

traditional treatment groups.

The study phases include: 1) Screening and baseline period: confirm whether patients are eligible for the study and create a record; decide whether trepanation and drainage should be performed by considering the condition of the disease and the imaging results; carry out randomized assignment and therapy. Eligible subjects will be randomly assigned to the traditional treatment group or MMA embolization group at a ratio of 1:1. 2) Follow-up period: visit patients for efficacy endpoints and safety endpoints at 30 days, 90 days, and 360 days post-procedure.

Figure 1. Schematic diagram of inclusion and randomization of subjects

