### **3. Sample Size Considerations**

The study hypothesizes that patients undergoing middle meningeal artery embolization may have lower symptomatic recurrence (in the trepanation/drainage group) and lower rates of symptomatic hematoma progression (in the non-surgical group) of subdural hematoma compared to patients who do not go MMA embolization. Two interim analyses will be conducted. With an expected symptomatic recurrence rate (trepanation/drainage group) / symptomatic progression rate (non-surgical group) after MMA embolization of 5% compared with 12% in the control group, and considering a loss to follow-up rate of 8%, a sample size of 722 cases with a two-sided alpha of 0.05 would yield 90% power.

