### 8.2.2. Analysis Methods

- The primary analysis will compare groups using the CMH chi-square test (the stratification factor is whether or not to perform trepanation/drainage was performed), summarize the 90-day recurrence (trepanation/drainage group) / progression rate (non-surgical group) for the MMA embolization group and the control group using the two-sided 95% CI (Clopper-Pearson method) and summarize the two-sided 95% CI for the difference in recurrence or progression rates between the two groups using the Miettinen-Nurminen method.
- Sensitivity analyses will use generalized linear mixed-effects model to calculate ORs and their 95% CIs for the comparison of recurrence or progression rates between the two arms, with group as fixed effect, site as random effect. Results of multivariable analysis will also be

presented, including treatment group, sex, age, surgical treatment strata (trepanation/drainage vs. no trepanation/drainage), any usage of antiplatelet or anticoagulant therapy, hematoma volume of baseline CT as covariates.

Enter Analysis Methods and Results Presentation

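### If multiple imputation runs, the SAP Appendix 3 code reports Rubin-pooled Wald intervals, not the Clopper-Pearson and Miettinen-Nurminen intervals named in SAP 8.2.2; the numerical effect is small

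*SAP*

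**What the plan says.** SAP 8.2.2 says that each group's 90-day rate is summarized "using the two-sided 95% CI (Clopper-Pearson method"), and that the interval for the difference is calculated "between the two groups using the Miettinen-Nurminen method". Table 1 of the SAP lists both as changes from the protocol.

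SAP 8.2.1 and Table 5 send the primary analysis to multiple imputation when more than 5% of the primary endpoint is missing. Below that level nothing is imputed and missing outcomes count as no event. SAP section 3 sizes the trial "considering a loss to follow-up rate of 8"%.

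The SAS sample in SAP Appendix 3 is the only place that says how imputed results are combined. It has two relevant blocks:

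- The block commented as Clopper-Pearson requests exact limits in PROC FREQ. It then gives PROC MIANALYZE "modeleffects proportion" with the variable `ase` as standard error.
- The block commented as `mn` requests Miettinen-Nurminen limits and saves them as `pdiffcls1`. It then pools "modeleffects risk" from the risk-difference table, again with `ase`. The saved limits are not read again.

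No text in the SAP says that the interval type changes under imputation.

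**The concern.** The prose and the code give different intervals for the same headline estimates. Rubin's rules applied to an estimate and its asymptotic standard error give an interval symmetric about the pooled estimate. Clopper-Pearson and Miettinen-Nurminen intervals are generally asymmetric at low event rates. A report produced from this code could name the two stated methods above limits that neither method produced.

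The form of the interval matters most near 5%, the rate assumed for the embolization arm. There a symmetric interval sits too low and covers less often than its nominal level.

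**Working it through.** **Inputs.** SAP section 3 gives event rates "after MMA embolization of 5% compared with 12% in the control group" and states that "a sample size of 722 cases with a two-sided alpha of 0.05 would yield 90% power". Protocol 3.1 gives the allocation: "Eligible subjects will be randomly assigned to the traditional treatment group or MMA embolization group at a ratio of 1:1".

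**The plan's own figure.** With pooled variance and no continuity correction, the number per arm is

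n = [1.960 × √(2 × 0.085 × 0.915) + 1.2816 × √(0.05 × 0.95 + 0.12 × 0.88)]² / 0.07² = (0.773 + 0.501)² / 0.0049, which rounds up to 332.

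The total is 664, and 664 / 0.92 = 721.7, or 722. The stated size is reproduced, with 361 randomized per arm and 332 observed after 8% loss.

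**Can imputation run?** The trigger is more than 0.05 × 722 = 36.1 missing endpoints. A loss of 8% would be 0.08 × 722 = 57.8, about 58. So it would run if endpoint missingness reached the planning allowance.

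**What the code computes.** For m imputations with mean estimate Q, mean squared standard error W and between-imputation variance B, PROC MIANALYZE gives Q ± t × √T, where T = W + (1 + 1/m)B. Here W comes from p(1 − p)/n for a rate, or the sum of the two arms' terms for the difference. That is a Wald variance. The exact and Miettinen-Nurminen limits do not enter.

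**Size of the shift.** I took 17/332 and 40/332 observed events (the planned rates, rounded). The 29 missing outcomes per arm were imputed from a draw of that arm's rate, with m = 20, and the pooled limits were averaged over repeated runs.

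| Quantity | Stated method, 332 observed per arm | Pooled as in the code | Shift in lower / upper limit (points) |
|---|---|---|---|
| Embolization rate | 3.01% to 8.07% | 2.75% to 7.51% | 0.26 / 0.56 |
| Control rate | 8.75% to 16.04% | 8.54% to 15.56% | 0.21 / 0.48 |
| Difference (points) | −11.37 to −2.74 | −11.16 to −2.68 | 0.21 / 0.06 |

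The text of SAP 8.2.1 gives 10 imputations and the code 20. With 10, the difference interval is −11.17 to −2.66, so that choice hardly matters here.

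A hand check on the 17 observed events: p = 0.0512 and SE = √(0.0512 × 0.9488 / 332) = 0.0121, so p ± 1.96 SE is 2.75% to 7.49%. Clopper-Pearson runs 2.1 points below the estimate of 5.12% and 2.95 points above it. The Wald interval runs 2.37 points each way.

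**Coverage.** On complete data with n = 361, exact Wald coverage is 94.2% at a true rate of 5% and 94.5% at 12%. Clopper-Pearson gives 97.1% and 95.7%. In simulation with 8% missing at random, the pooled Wald interval covers about 93.8% for the 5% arm, and its upper limit falls below the true rate in about 5.0% of trials. The pooled interval for the difference covers about 94.9%. Pooling the 5% arm on the logit scale gives about 95.6%.

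**P-value.** The CMH statistic is transformed (Wilson-Hilferty) and pooled in a separate block of Appendix 3. It does not use these standard errors.

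**The case against.** The best case for leaving the code alone has four parts.

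1. *Imputation may never run.* The 8% is a sample-size allowance for loss to follow-up, not a forecast of missing primary endpoints. SAP 8.2.1 and Table 5 reduce missingness: a recorded operation settles the endpoint, death within 104 days counts as an event, and out-of-window measurements are used in the primary analysis. Protocol 7.1.4 also says that missing values are not imputed, although the later SAP plans otherwise. If nothing is imputed, the code in SAP 8.2.3.1 does request the stated limits. This stands: the documents make imputation possible, but do not show it to be the expected route.
2. *The comparison is unharmed.* This also stands. A reader might infer that Wald limits flatter embolization. The pooled point estimates do not depend on the interval type, the rate limits move down in both arms, and the upper limit of the difference moves marginally towards zero.
3. *Clopper-Pearson is conservative, and its limits cannot simply be averaged by Rubin's rules.* True, so any repair under imputation uses a different interval. It follows that the SAP must name the interval, not that the mismatch can stay.
4. *The code is only a sample.* True, but no other text specifies the pooling, so in practice the sample is the specification.

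Two stronger readings also fail. One is serious under-coverage in subgroups. Complete-data Wald coverage at 5% is 91.2% with n = 166 but 94.0% with n = 180, so the lower figure is a low point caused by discreteness. The other is that the code is bound to report the non-event rate and a difference of reversed sign. The code names no event level, but the SAP does not state how `aval` is coded beyond limits of 0 and 1, so the outcome depends on coding and software defaults. A rate near 95% would also be noticed.

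**Conclusion.** The mismatch is real and minor. If more than 5% of primary endpoints are missing, the code yields normal-approximation intervals where SAP 8.2.2 names Clopper-Pearson and Miettinen-Nurminen. The cost is a wrong label and slight under-coverage of a descriptive rate near 5%. Neither the conclusion on the difference nor the CMH test changes at the planned rates.

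The sizes assume event rates of 5% and 12%, 8% missing in each arm, missingness at random within arm, and imputation from the arm's observed rate. The SAP's own imputation step (MCMC with covariates, then rounding) was not replicated.

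**What to change.** - Under imputation, pool each arm's rate on the logit scale and back-transform the limits, and say so in SAP 8.2.2.
- State in SAP 8.2.2 that the imputed risk difference has a Rubin-pooled normal-approximation interval. Its coverage is adequate, so no other method is needed.
- Relabel the comments and outputs in SAP Appendix 3 to match. Keep the names Clopper-Pearson and Miettinen-Nurminen for the analysis without imputation.
- State the coding of `aval`. If 1 means an event, set that level explicitly in the BINOMIAL option and take the matching risk-difference column. Both steps are needed, because setting the level for the rate does not alter the column used for the difference.

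The cost is a few lines of code and two sentences of text, with slightly higher upper limits for the rates than the present code would give.

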## 8.2. Specifications of Primary Efficacy Endpoints Analyses

### 8.2.1. Definitions and Derivations

- **Symptomatic** SDH recurrence (in the trepanation/drainage group) refers to a situation in which the maximum thickness of hematoma of patients exceeds 10 mm, combined with neurological symptoms, or the need for repeat surgery.
- Symptomatic SDH progression (in the non-trepanation/drainage group) refers to a situation in which the maximum thickness of increases by more than 3 mm compared with baseline, combined with neurological symptoms, or the need for surgery.
- The results of central imaging evaluation and analysis of CT/MRI examinations required for the determination of the subject 's primary endpoint in this study will be presented in tables and listings, respectively. Central image evaluation will be performed by the independent Core Lab. Evaluation of neurological symptoms will be derived from the Outcome Assessment Committee (OAC) review data.
- It should be noted that if there is a record of reoperation in participants who have undergone trepanation/drainage, and there is a record of surgical treatment in subjects who have received medical therapy without trepanation/drainage, the occurrence of the primary endpoint can be directly determined, and hematoma thickness or neurological symptoms are no longer required.
- In case of non-negligible amounts of missing data (>5%), we will use the MCMC method based on the Missing at random (MAR) assumption to impute missing data. The regression model will include group, sex, age, BMI, baseline mRS score and baseline maximum

hematoma thickness. The number of imputations is 10, seed=1234, nbiter=200. SAS code examples for multiple imputation will be provided in Appendix 3.

- Hematoma recurrence (trepanation/drainage group) or symptomatic hematoma progression (non-surgical group) at day 90 will be analyzed as follows. If there is any discrepancy between EDC and central imaging assessment scan date in the determination of visit window, the date determined by central imaging assessment shall prevail.

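### The Appendix 3 multiple-imputation code does not carry the imputed 90-day outcome into the primary analysis, and its risk-difference and CMH steps do not separate the two rows it creates per patient

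*SAP*

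**What the plan says.** SAP 8.2.1 sets the trigger: "In case of non-negligible amounts of missing data (>5%), we will use the MCMC method". It then refers the reader onward: "SAS code examples for multiple imputation will be provided in Appendix 3". Table 5 makes multiple imputation the primary-analysis rule for patients without 90-day data. Section 8.2.2 compares the arms with a CMH test stratified by trepanation/drainage and gives a Miettinen-Nurminen interval for the risk difference. Read together, these sections plan one 90-day outcome per patient, imputed where missing.

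The code in Appendix 3 (12.3) proceeds as follows.

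- PROC MI imputes from the list "var sex age bmi basemrs basemth aval". The outcome in that list is `AVAL`.
- A transpose, "proc transpose data=im2 out=im2_t(rename=(_name_=avisit coll=aval", is keyed "by _imputation_ trtan usubjid siteid" and takes `v1` and `v2` as its only analysis variables.
- The counts for the Clopper-Pearson step are grouped "by _imputation_,trtan,avisit", so that step keeps the two rows apart.
- The risk-difference step, "tables trtan *aval / commonriskdiff (cl=score test=score) riskdiff (cl=mn", runs by imputation number only.
- The CMH step, "tables strata*trtan*aval/cmh", also runs by imputation number only.

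**The concern.** The code departs from the text of 8.2.1 and 8.2.2 in three ways. The variable that is imputed is not the one analysed. The analysed file holds two rows per patient where the text plans one outcome. The CMH step needs a stratum variable that the file does not contain.

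The primary risk difference and the primary test are at stake in the situation for which the imputation was written. Appendix 3 is also the only place in the SAP that says how CMH results are combined across imputations (a Wilson-Hilferty transformation followed by PROC MIANALYZE). A programmer would therefore have to start from this code.

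**Working it through.** **Inputs.** The design figures are 722 patients, 1:1, 12% versus 5%, two-sided alpha 0.05, 90% power and 8% loss (SAP section 3; protocol 7.1.3). The imputation trigger is more than 5% missing (SAP 8.2.1, Table 5). Variable lists and BY statements come from SAP Appendix 3.

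**The plan's own figure.** With pooled variance and no continuity correction, the average rate is 0.085 and

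n per arm = [1.960 × √(2 × 0.085 × 0.915) + 1.282 × √(0.12 × 0.88 + 0.05 × 0.95)]² / 0.07² = (0.773 + 0.501)² / 0.0049, about 331.5, rounded up to 332.

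The total is 664, and 664 / 0.92 = 721.7, so 722 is reproduced. The trigger is 0.05 × 722 = 36.1, that is, 37 or more missing endpoints. An 8% loss would be about 58.

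**Tracing the code.**

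1. PROC MI completes `AVAL`. `v1` and `v2` are not in its variable list, so it leaves them as they were.
2. `AVAL` is neither a key nor an analysis variable of the transpose. The `AVAL` in the output file `im2_t` is therefore the old `v1` and `v2`, and every later step uses `im2_t` or counts made from it.
3. The keys are imputation, arm, patient and site, so there are two rows per patient per imputation. `STRATA` is not carried over.
4. The binomial and GLIMMIX steps run by visit (the variable name is misspelt in the GLIMMIX block). The risk-difference and CMH steps have no visit in the BY statement or the table request, and no WHERE.
5. PROC FREQ drops missing values. A patient with both values counts twice, with one value once, and with neither not at all.
6. The CMH step calls `STRATA`, which `im2_t` lacks, so it stops with an error.

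**Emulating the data flow.** The emulation used 722 patients, 59 of them with both `v1` and `v2` missing, and 20 imputations. `im2_t` held 2 × 722 = 1,444 rows per imputation, of which 2 × (722 − 59) = 1,326 were non-missing and used. The risk difference was identical in all 20 imputations, so between-imputation variance was zero. With the imputed `AVAL` that variance was 3.7 × 10⁻⁵.

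**Size for the risk difference.** With 332 evaluable per arm and one row each, the 95% half-width is 1.96 × √[(0.1056 + 0.0475) / 332] = 4.2 points. If `v1` equals `v2` for every patient, doubling the rows gives 4.2 / √2 = 3.0 points, and true coverage is 2Φ(1.96/√2) − 1 = 83%.

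**Size for the CMH test, if `STRATA` were restored and nothing else changed.** Assume `v1` and `v2` are binary outcomes with equal variance and correlation rho, both observed. The true variance of the comparison is (1 + rho) times what the test assumes, so type I error = 2[1 − Φ(1.96/√(1 + rho))].

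| rho | 1.96/√(1 + rho) | type I error |
|---|---|---|
| 0.25 | 1.753 | 8.0% |
| 0.5 | 1.600 | 11.0% |
| 0.8 | 1.461 | 14.4% |
| 1.0 | 1.386 | 16.6% |

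Simulation agrees. It took `v1` and `v2` as day-90 and day-360 outcomes, an assumed 70/30 stratum split and a common 8.5% day-90 event rate. With complete data and `v1` equal to `v2`, error was 16.5%. With 8% missing at day 90 and 0%, 3% or 8% further events, it was 16.2%, 13.6% and 13.2%. One observed day-90 row per patient gave 4.6% to 5.4%.

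**The case against.** The strongest defence is that the block is labelled a sample, while the governing text in 8.2.1, 8.2.2 and Table 5 correctly plans one outcome per patient. The block could not run unaltered in any case, and some of its oddities may come from reading the PDF. This limits the claim without removing it. The point rests on variable lists and BY statements, not on spelling, and no other part of the SAP says how the CMH results are to be pooled.

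A kinder reading takes `AVAL` in the PROC MI list as shorthand for `v1` and `v2`. The imputation would then work, but the risk-difference and CMH steps would still pool two rows per patient.

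Four parts of the defence stand.

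- A reader might infer that the printed code yields a primary p-value with inflated type I error. It does not, because the CMH step fails first. The inflation needs a partial repair that restores `STRATA` and leaves the visits pooled.
- `v1` and `v2` are undefined. In the study flow chart (SAP Appendix 1), V1 and V2 are the baseline and discharge visits. Rho cannot be derived from the documents, which is why a range is shown. If the input file has no such variables, the transpose itself fails, and the imputed `AVAL` is unused either way.
- A reader might infer that every patient is counted twice, on 1,444 rows. As printed, that holds only if no `v1` or `v2` value is missing.
- The 8% is a planning allowance for loss to follow-up, not a forecast of missing endpoints. Deaths count as events, out-of-window measurements are used, and recorded surgery alone settles the endpoint. All three reduce missingness, so the 5% trigger may not be reached.

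**Conclusion.** The concern holds as a defect in the specified code. As printed, no imputed value reaches the analysis, the risk-difference step double counts patients who have both values and drops those who have neither, and the CMH step cannot run. These conclusions follow from the code, given only that `v1` and `v2` exist in the input file.

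The sizes are conditional. Type I error of about 8% to 17% assumes two binary outcomes with rho between 0.25 and 1 and `STRATA` restored without a visit restriction. The fall in half-width from 4.2 to 3.0 points, with 83% coverage, is the extreme case in which `v1` equals `v2`.

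A reader might conclude that a reported primary result is wrong. The documents do not support that: the code is a sample, it applies only above 5% missing, and they do not show which program was run.

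**What to change.** Drop the transpose of `v1` and `v2`. Keep one row per patient per imputation, with the imputed 90-day `AVAL` and `STRATA`, and run the binomial, risk-difference, CMH and GLIMMIX steps on that file by imputation number. Remove the visit variable from the binomial and GLIMMIX steps and from their pooling.

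If two visits are wanted, all of the following are needed:

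- put both outcomes in the PROC MI variable list;
- carry `STRATA` through the transpose;
- sort by imputation number and `AVISIT`;
- add `AVISIT` to the BY statements of the risk-difference and CMH PROC FREQ steps;
- add `AVISIT` to the BY statements of their PROC MIANALYZE steps, with the input sorted to match. Otherwise the two visits would be pooled as if they were extra imputations.

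In the same edit, reconcile the number of imputations, which is 10 in section 8.2.1 and 20 in the code.

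The cost is a few lines of code before database lock. Design, data collection and sample size are unaffected.
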